This also begs the question if antibiotics are truly a necessary and beneficial component in the preparation for a sterile root canal. Prior laboratory in-vitro studies have determined that disinfection protocols have a profound effect on stem cells of the apical papilla (SCAP) as well as dentine microhardness. Yassen et al demonstrated that dentine microhardness was significantly reduced when triple or double antibiotic mixtures were used for treatment of dentine compared to Ca(OH)_2 (20). Antibiotic paste formulations used in RET procedures were found to be directly toxic to stem cells even at concentrations as low as 1% of doses currently used in treating patients, while conversely dentin conditioning with Ca(OH)_2 was found to promote SCAP survival and proliferation (21, 22). This may well have clinical implications impacting fracture resistance and SCAP survival in immature permanent teeth with already compromised root thickness.

Given that this procedure (Regenerative Endodontic Therapy using revascularization via blood clotting method) has been carried out in children in Singapore since 2007, and a retrospective study is in progress, it is considered timely to conduct a prospective randomized controlled study to evaluate the need for antibiotic pastes and the outcome and success of RET.

2.0 Research questions/Aims and Objectives:

Research questions:

1. Are there differences between treatment outcomes of a 2-Mix antibiotic paste (Ciprofloxacin and Metronidazole) vs disinfection with the currently accepted multiple-visit protocol in non-surgical root canal treatment (i.e. disinfection with NaOCl solution followed by Ca(OH)₂ as inter-appointment dressing) with respect to:
 - i. Resolution of apical periodontitis.
 - ii. Thickening of dentinal walls and/or continued root development with or without apical closure.
2. Which are the baseline characteristics which could predispose a case to successful outcome?
3. Will discolouration of teeth occur and to what extent?

Primary aim

1. To assess frequency of periapical healing in the two sets of experimental protocols.
2. To study the differences in qualitative and quantitative increase in root dimensions of different protocols, by evaluating continued root development and thickening of dentinal walls.

Secondary aims

1. To evaluate if tooth discolouration occurs by evaluating the changes in tooth colour following treatment using the different protocols.

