- The antibiotics will be placed into the root canal with a carrier and pluggers to completely fill the root canal system; Controls will be filled with Ca(OH)_2 , placed in according to currently employed procedures.
- The root canal will then be hermetically sealed with a sterile cotton pledge, IRM and a glass ionomer cement to prevent any coronal leakage or contamination of the root canal with oral microorganisms.
- The patient will then be discharged, and given an appointment to return for the next step of treatment in 4 weeks \pm 7 days.

Second Treatment Visit:

- The tooth will be examined and evaluated for clinical signs of an abscess, increased mobility and presence of the existing coronal seal restoration prior to commencement of local anaesthesia and rubber dam procedures.
 - If any of the above is present, a repeat session of disinfection is necessary and the first treatment visit procedures will be repeated until there is no clinical presence of an abscess or sinus tract. Information on number of additional disinfection visits will be recorded.
 - The operator/assistant will refer to patient ID recorded in treatment notes, and access the Intervention Log and double check the intervention group assigned to the patient prior to preparing the medicament to be used.
- Local anaesthesia without a vasoconstrictor will be administered and the tooth will be isolated and re-accessed as described above.
- The antibiotic mixture will be flushed out of the root canal by irrigation until solution runs clear with sodium hypochlorite. Ca(OH)_2 dressing will be removed by essentially the same procedure.
- The root canal will be irrigated slowly with 10ml 17% EDTA.
- Following this, the root canal will be thoroughly dried with paper points.
- A sterile 23-gauge needle or sterile file with a length of 25mm will be inserted beyond the working length and past the confines of the root canal into the periapical tissues to intentionally induce bleeding into the root canal. The bleeding is then allowed to fill the root canal.
- Once the root canal is filled with blood, a moist cotton pledge will be placed in the root canal below the cementoenamel junction (CEJ), and a clot will be allowed to form in the root canal.
- Once the clot is formed, the coronal portion of the root canal will be cleaned (with a new sterile cotton pledge moistened with saline) to remove any remnants of blood, which could cause discolouration in future

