3.4.2.4 Radiographic Analysis

Measurements of digital radiographs will be carried out using the measurement tool available in the VixWin digital radiography viewing software. Calibration of the measurements (based on the known width of the digital film) will be done prior to carrying out of quantitative measurements. Digital radiographs will be read in a darkened room, on a standardized monitor (DELL E2213H 1920 x 1080 Pixel Resolution 22" LCD Display) screen and computer with Windows Operating System (OS).

For length measurements, the point of reference will be the cement-enamel junction (CEJ) and Measurement ideals are referenced from the article by Bose *et al*(10), Chugal *et al* 2001(25) and Yu *et al* 2012(26). Below are the set definitions and proposed criteria which will be used for measuring the abovementioned parameters for radiographic analysis:

1. Size of periapical lesion,
 - Measured using the periapical index (PAI) scoring system (27)
2. Resolvement of periapical lesion;
 - Defined as the complete absence of existing periapical radiolucency as compared with pre-operative radiograph
3. Root length

- Quantitative outcome: Measured in millimeters (mm) as a straight line from the CEJ to the radiographic apex of the tooth;
- Binary outcomes: Comparison of increase in root length (Yes/No)
- Both pre and post-operative (measured during the recall visits) will be recorded.

4. Dentinal wall thickness measurements (at apical and mid root)
 - Quantitative outcome: Measured in millimeters (mm) at the apical one third of the tooth;
 - Binary outcomes: Comparison of increase in dentine wall thickness (Yes/No)
 - The dentinal wall thickness for both the preoperative and recall images will be measured at the level of the apical one third of the preoperative root canal length measured from the CEJ. The root canal width and the pulp space will be measured at this level, and the remaining dentin thickness will be calculated by subtracting the pulp space from the root canal width
5. Width of apex;
 - Measured in millimeters (mm) as the distance between the inner sides of the open apex
 - Binary outcomes: Comparison of decrease in width of apex (Yes/No)
6. Continued root development;
 - Measured as Postoperative root length minus Pre-operative root length (in millimeters) (mm); percentage change will also be calculated
7. Closure of apex;
 - Measured by means of visual identification; defined as approximation of the inner sides of the root tips.

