8. Pulp canal obliteration
 - Defined as hard tissue deposited along the wall of the root canal which fills most of the pulp canal as detected through comparisons with pre-operative radiographs.

Since this study involves primarily young subjects (i.e. children), to account for possible clinical variations, both binary and quantitative outcomes will be collected. This is to account for clinical variations which may occur during the treatment process. The following parameters will be evaluated:

- Reduction in size or resolution of periapical lesion
- Pulp canal obliteration
- Anomalies detected - any deviation from the norm, e.g. pulp canal obliteration, ingrowth of osteoid (bone)-like tissue etc.
- Continued root development and changes in dentinal root thickness and width of apex will be quantified using VixWin and Image J software.

Two independent assessors will be involved in the clinical and radiographic analysis. Prior to commencement of the analysis, the investigators will undergo training and calibration. All analysis will be carried out separately by the assessors, and results will be compared.

All radiographs will be randomly shown to the examiners who will be asked to score the test parameters. All available radiographs will be evaluated at the same time, and using the same computer under standardized monitor display configuration and lighting conditions. All measurements will be repeated after 1 week, and the mean of the 2 replicates will be considered as the final value. In cases where there is doubt or a large discrepancy between readings, both investigators will discuss and come to an agreement. All patient identifiers will be removed from the radiographs prior to radiographic analysis to prevent potential measurement bias.

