4.5. Statistical methods

All analysis will be carried at a tooth level, where each tooth will be accounted for as an individual case. Descriptive statistics (both discrete and non-discrete variables), which will include means, standard deviations, frequencies and percentages will be determined. Data will be checked for homogeneity of variance prior to application of statistical tests. Appropriate correlation and regression analysis will be

employed in consultation with a biostatistician. Inter and intra-operator variability scores will be evaluated using Kappa statistics. The significance level will be set at $p<0.05$. All data will be analyzed using SPSS Statistical Package (IBM SPSS Statistics).

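### Dentine thickness is defined as root canal width minus pulp space, which are the same space; mid-root has no rule; and kappa is the only agreement statistic for readings in mm

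*Protocol*

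**What the plan says.** Section 2.0 makes root dimensions the second primary aim, to be studied by "evaluating continued root development and thickening of dentinal walls". Section 3.4.2.4 then lists the measurement definitions.

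- **Formula.** Item 4 has two widths measured at one level, after which "the remaining dentin thickness will be calculated by subtracting the pulp space from the root canal width".
- **Level.** The item is headed "Dentinal wall thickness measurements (at apical and mid root". Its quantitative line reads "Measured in millimeters (mm) at the apical one third of the tooth", and the rule for locating the level also refers only to the apical third.
- **Replicates.** Two assessors read separately. "All measurements will be repeated after 1 week, and the mean of the 2 replicates will be considered as the final value".
- **Agreement.** Section 4.5 says: "Inter and intra-operator variability scores will be evaluated using Kappa statistics". It names no variant of kappa, does not restrict it to categorical items, and names no other agreement statistic.

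**The concern.** There are two points of different weight.

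**Definition of dentine thickness (wrong as written).** A wall thickness needs an outer and an inner boundary. Item 4 names two terms for the inner space and never mentions the outer root surface. If assessors silently substitute another width, the reported measure is no longer the one in the protocol, and a reader cannot reproduce it from the text. Because mid-root stands in the heading only, a reader also cannot tell whether one or two thickness outcomes were planned.

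**Agreement statistic (free improvement).** Kappa is designed for categories. Root length is the outcome that sizes the trial (section 3.5), and it is read in mm, as are wall thickness and apex width. Unweighted kappa on such readings depends on how finely they are rounded as well as on how well the readers agree. No form of kappa states the reading error in mm.

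**Working it through.** **1. What the formula returns**

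The protocol's own use of the terms:
- In section 3.4.2.2, second treatment visit, the root canal is a lumen: "The bleeding is then allowed to fill the root canal".
- In section 3.4.2.4, item 8, pulp canal obliteration is "hard tissue deposited along the wall of the root canal which fills most of the pulp canal". Tissue on the wall of the root canal fills the pulp canal, so the two terms name one lumen.
- No definition in section 3.4.2.4 mentions outer root width.

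Let R be the outer root width and P the canal (pulp space) width at the chosen level.
- Literal rule: P − P = 0 mm, before and after treatment. No thickening could be shown.
- Root canal width read as outer root width: R − P, the sum of the two walls, i.e. twice the mean single wall.
- Root canal width read as the canal outline before treatment: preoperative P minus current P. This gives new deposit only and is 0 before treatment, which fits poorly with a thickness that is said to remain.

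The second reading is the natural one, but the text does not state it.

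**2. Levels**

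| Part of item 4 | Apical | Mid-root |
|---|---|---|
| Heading | yes | yes |
| Quantitative line | yes | no |
| Rule for locating the level | yes | no |

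No mid-root rule appears elsewhere in the protocol.

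**3. Kappa on mm readings**

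The protocol gives no between-tooth SD, reading error or rounding step for root length, so all three are assumptions: between-tooth SD 2 mm; single-reading error SD s from 0.1 to 0.5 mm; rounding step w of 0.1 or 0.5 mm. The method was a simulation of 2,000,000 teeth, each with two readings with independent errors, rounded to w. Kappa = (po − pe)/(1 − pe), where po is observed and pe is chance agreement. ICC = 2²/(2² + s²) = 4/(4 + s²).

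| s (mm) | ICC | w = 0.1: unweighted / linear / quadratic | w = 0.5: unweighted / linear / quadratic |
|---|---|---|---|
| 0.1 | 0.998 | 0.26 / 0.95 / 0.997 | 0.76 / 0.95 / 0.993 |
| 0.2 | 0.990 | 0.13 / 0.90 / 0.990 | 0.53 / 0.90 / 0.985 |
| 0.3 | 0.978 | 0.08 / 0.85 / 0.978 | 0.38 / 0.85 / 0.973 |
| 0.5 | 0.941 | 0.04 / 0.76 / 0.941 | 0.22 / 0.76 / 0.937 |

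Hand check of the unweighted value at s = 0.5, w = 0.1. For a small step, po ≈ w/(2s√π) = 0.1/1.772 = 0.0564. With total SD √4.25 = 2.062, pe ≈ 0.1/(2 × 2.062 × √π) = 0.1/7.308 = 0.0137. Kappa ≈ (0.0564 − 0.0137)/(1 − 0.0137) = 0.043, in line with the table.

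A separate run with 60 teeth per data set gave the same pattern: at s = 0.2, mean unweighted kappa was 0.12 in 0.1 mm steps and 0.53 in 0.5 mm steps. With between-tooth SD 1 mm and w = 0.1, s = 0.2 gives ICC 0.962, unweighted 0.12 and quadratic 0.961; s = 0.3 gives 0.917, 0.07 and 0.917.

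On the mm scale, the 95% limits of agreement between two single readings are ±1.96 × √2 × s, from ±0.28 mm (s = 0.1) to ±1.39 mm (s = 0.5). No kappa conveys that figure.

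**The case against.** **On the formula.** Item 4 takes the difference between its two terms, so it plainly treats them as two distances, and its title says what is wanted. Assessors are trained, calibrated and blinded, and whatever they measure applies to both arms alike. Section 3.4.2.4 also points to cited articles for its measurement conventions. Most of this stands: a column of zeros is unlikely and no bias between arms follows. None of it repairs the written rule, and a reference to other articles does not correct a formula that the protocol then writes out itself.

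**On mid-root.** Appendix F, the data collection sheet, is not shown and may have a mid-root field. That is possible, but a field on a form would not supply the missing rule for locating the level.

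**On one wall or both.** The sum of both walls differs from the mean wall by a constant factor of 2, so tests, percentage change and the Yes/No outcome are the same. That is right; stating which is reported matters only for reading values in mm.

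**On kappa.** Many readings are categorical (PAI, resolution, apex closure, the Yes/No items), and kappa suits these. The choice of ICC and of kappa variant is often left to an SAP, which is not at hand. The protocol does not say that kappa will be computed on raw mm values, and the simulation rests on assumed inputs. The widest contrast, 0.04 against 0.94, sets unweighted kappa in 0.1 mm steps against quadratic weighting at the largest assumed error. This is fair as far as it goes, and it is why the point is graded a free improvement. The sentence in section 4.5 still covers all inter- and intra-operator variability without restriction.

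**Conclusion.** The concern holds.

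**Item 4 of section 3.4.2.4 is wrong as written.** Taken literally, it gives about 0 mm. With the likely intended outer root width, it gives both walls together. The heading conflicts with the quantitative line and the locating rule on whether mid-root is measured. What is at stake is the definition and reproducibility of a primary-aim measure; no bias between arms has been shown. This rests on the protocol's own use of its terms and on no outside figure.

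**Kappa as the sole agreement statistic fits the mm readings badly.** Under the stated assumptions, readings with an ICC of 0.94 to 0.998 give unweighted kappas from 0.04 to 0.76, depending on error and step. Quadratic-weighted kappa stays close to the ICC. This affects the reliability report only, not the between-arm comparison of root length or the sample size.

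The item 4 wording should be corrected; the agreement statistics are worth adding at the same time.

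**What to change.** **Section 3.4.2.4, item 4.** Define remaining dentine thickness as the outer root width minus the width of the pulp space (canal) at the stated level, and say that this is the sum of both walls. Then either add mid-root to the quantitative line with a rule for locating it, or remove it from the heading.

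**Section 4.5.** For root length, wall thickness and apex width, report ICC with Bland-Altman limits of agreement in mm, between assessors and between the two reading sessions. Use weighted kappa (weights stated) for PAI and kappa for the Yes/No items. ICC depends on the spread between teeth, so it should be read together with the limits of agreement.

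**Cost.** A few lines of wording and of analysis, on replicate readings already planned. No new films or visits. Keeping mid-root adds one measurement level per film.

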3.0 Materials and Methods

3.1 Study Design

This will be a multi-center, parallel-group allocation (1:1), randomized controlled trial of treatment carried out on non-vital immature permanent teeth in children using revascularization via blood clotting technique. Both the patient and the assessors will be blinded to the intervention. The clinical study will be carried out at the School Dental Service, Health Promotion Board and NUH Dental Centre over a period of 3 years.

Regenerative Endodontic Therapy (using revascularization via blood clotting method) will be defined as any permanent tooth which has undergone at least a two-stage procedure involving:

- a. Disinfection using sodium hypochlorite irrigation and placement of inter-appointment dressing (antibiotics or calcium hydroxide), followed by
- b. Procedures which involve inducing bleeding and blood clot and hence intentional initiation of proliferation of stem cells of the apical papilla (SCAP) into the root canal.

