3.4. Participants

3.4.1 Inclusion and Exclusion criteria

The inclusion criteria are as follows:

1. Patients aged 6-16 years of age
2. Patients who are fit and healthy or with ASA 1 or ASA 2 medical conditions
3. Patients with cooperation level that would allow treatment under local analgesia, application of rubber dam isolation and taking of intraoral radiographs.
4. Patients with permanent premolars that have incomplete root formation with an open apex of greater than 1mm width as observed radiographically and of single root canal morphology (23)
5. Patients with single rooted immature permanent teeth having one of the following pulpal and periapical diagnosis:
 - a. Pulpal
 - i. Necrotic pulp
 - ii. Symptomatic and inflamed pulp not expected to heal. During attempted Cvek or cervical pulpotomy procedures, if the pulpal bleeding does not stop with direct pressure within 5 minutes, pulpectomy will be carried out and the patient will be recruited for RET procedures.
 - b. Periapical
 - i. Symptomatic apical periodontitis (with or without a radiographic apical lesion)
 - ii. Asymptomatic apical periodontitis (with a radiographic apical lesion)
 - iii. Acute apical abscess
 - iv. Chronic apical abscess

Teeth will be deemed non-vital if either are non-responsive to sensibility tests (i.e. EPT and cold tests), and/or present with signs and symptoms of non-vitality (e.g. swelling and abscess).

The exclusion criteria are as follows:

1. Patients aged > 16 years of age.
2. Patient with known allergies to Ciprofloxacin (or any fluoroquinolones class of antibiotics) or Metronidazole antibiotics.
3. Patients with medical conditions and/or receiving medications that would affect:
 - a. Their body's ability to heal e.g. Diabetes; or
 - b. Their ability to clot efficiently, e.g. Haemophilia
4. Patients with risk of developing infective endocarditis or immune compromised patients.
5. Patients with non-vital permanent premolars where root development is already deemed to be completed (i.e. foramen size of 0-1.0mm diameter as determined radiographically).
6. Impacted or horizontally tilted teeth.
7. Concurrent signs of irreversible pathological root resorption determined radiographically, e.g replacement or internal root resorption, which could otherwise affect the prognosis of the tooth.
8. Uncooperative patients, or those unable to cope with treatment under local anaesthesia, rubber dam isolation and taking of intraoral radiographs.

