3.5 Sample size calculation

This sample size is likely to be achievable given the expected number of cases that will be available in the clinics employed in this proposal. Retrospective data available from the School Dental Service, Health Promotion Board showed that RET treatment was provided to 78 patients (with 85 teeth) over a period of 3 years 6 months (Mar 2009 to Dec 2012). 77.2% of these teeth were mandibular premolars, 13.9% were maxillary incisors, and 8.9 % were maxillary premolars. Of these, 69.4% (n=59) had successful outcomes with closed apices following RET treatment, 7.1% (n=6) showed signs of increased root length and dentine wall thickening but were still undergoing review, 5.9% (n=5) did not show signs of root growth but demonstrated resolution of periapical pathology, 8.2% (n =7) had unfavourable outcomes with apices remaining open and signs of periapical pathology, and 9.4% (n=8) were loss to follow up.

The proposal will be for a sample size of 30 teeth per group, i.e. total estimated recruitment is 60 teeth. The sample size proposed is calculated based on data obtained from a published paper by Bose et al (2009). The sample size is estimated based on changes in root length as the primary outcome measure. Using a 2-sided sample test, assuming a mean difference between the groups of 1.5 and SD of 2, (at a significance level of 0.05 and 80% power), the sample size required is 30 subjects per group, i.e. 60 subjects in total. It is our hope that a multi-centre approach will help increase the caption group and thus increase patient numbers.

This is in agreement with sample size proposed in existing on-going randomized control trials which are registered on the Clinical Trial database website: www.clinicaltrials.gov. The clinical trials have similar age-range of potential patients as the proposed study.

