6.2. Ensuring patient return for reviews

As this is a randomized controlled clinical study, it is possible that patients may not return for recalls following completion of procedures, resulting in drop outs. As such, a 10% margin for drop outs has been assumed in the power calculation. Intention to treat analysis will also be carried out.

Patients enrolled in the study will be followed up closely, and appointments at appropriate intervals as specified in the protocol will be made. Patients will be reminded to attend the review visits 2 days in advance via telephone or SMS. Treatment rendered and review visits will not be charged.

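### The sized outcome, root-length change, has only an unadjusted comparison described for it; naming pre-operative root length as a covariate would cost nothing and generally improve precision

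*Protocol*

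**What the plan says.** Section 3.4.2.4 lists how each radiographic parameter is measured. Root length (item 3) is taken in mm and recorded both pre-operatively and at recall. Continued root development (item 6) is "Measured as Postoperative root length minus Pre-operative root length (in millimeters) (mm); percentage change will also be calculated". Section 3.4.2.3 places the final outcome at the 18-month review.

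Section 3.5 ties the size of the trial to this quantity: "The sample size is estimated based on changes in root length as the primary outcome measure". The method is given as "Using a 2-sided sample test, assuming a mean difference between the groups of 1.5 and SD of 2", with the result "at a significance level of 0.05 and 80% power), the sample size required is 30 subjects per group, i.e. 60 subjects in total". No covariate is mentioned. Section 3.1 gives the design as a "parallel-group allocation (1:1), randomized controlled trial", and section 4.1 describes blocked randomisation within each centre, with no stratification by stage of root development.

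Section 4.5 does not name a test or model for comparing the arms. It provides for descriptive statistics, a check on homogeneity of variance, and suitable correlation and regression analysis to be settled with a biostatistician. No section names baseline root length as a covariate, and none excludes it.

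**The concern.** How much a root can still grow plausibly depends on how far it has already developed. Entry is open to "Patients aged 6-16 years of age" and to any premolar with an apex wider than 1 mm, so the teeth may differ in starting length. Section 6.3 also accepts that distortion and angulation may differ between pre- and post-operative films.

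A raw change score carries the full measurement error of the pre-operative film. With equal variances it is negatively correlated with the baseline value. A two-sample test on change therefore leaves in the residual some variation that the pre-operative length, already on file, could explain. Percentage change does not solve this, because it divides by the same baseline measurement.

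What is at stake is precision in a trial of 60 teeth, and clarity about which version of the root-length result is the main one.

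**Working it through.** **Inputs from the protocol.** Difference 1.5 and SD 2 (section 3.5), two-sided alpha 0.05, 80% power, 30 per group, 1:1 allocation.

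**Assumptions, because the protocol does not say.** The unit is mm. The SD of 2 is the SD of the change. Pre- and post-operative root length have equal variance. The pre-post correlation rho is unknown, so a range is shown.

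**Step 1: reproduce the plan's figure.** For an unadjusted two-sample comparison,

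n = 2 × SD² × (1.960 + 0.842)² / difference² = 2 × 4 × 7.85 / 2.25 = 27.9, so 28 per group.

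The noncentral-t calculation gives 29. Both are close to the stated 30, which supports reading the sizing test as unadjusted. At 30 per group the standard error of the difference is 2 × √(2/30) = 0.516, and t-based power is 81.5%.

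**Step 2: variance with and without baseline.** Let s² be the common variance of root length.

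- Variance of the change: 2s²(1 − rho).
- Residual variance after adjusting for baseline: s²(1 − rho²).
- Ratio: (1 − rho²) / (2(1 − rho)) = (1 + rho)/2.

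The residual SD after adjustment is therefore 2 × √((1 + rho)/2).

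**Step 3: power at 30 per group.**

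| rho | variance ratio | residual SD | n per group for 80% (normal) | power at 30 (t) | implied SD of root length |
|---|---|---|---|---|---|
| unadjusted | 1 | 2.000 | 28 | 81.5% | – |
| 0.5 | 0.75 | 1.732 | 21 | 91.0% | 2.00 |
| 0.7 | 0.85 | 1.844 | 24 | 87.2% | 2.58 |
| 0.8 | 0.90 | 1.897 | 26 | 85.3% | 3.16 |
| 0.9 | 0.95 | 1.949 | 27 | 83.4% | 4.47 |
| 0.95 | 0.975 | 1.975 | 28 | 82.5% | 6.32 |

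The last column is 2/√(2(1 − rho)), the SD of root length that each rho requires if the change has SD 2. Charging the model one degree of freedom and the usual small inflation for estimating the slope costs under one percentage point: 90.5% at rho 0.5, 84.7% at rho 0.8 and 81.8% at rho 0.95. None of these falls below 81.5%.

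**Step 4: where the gain comes from.** With equal variances, the slope of change on baseline is −(1 − rho). At rho 0.5 the implied baseline SD is 2, so the baseline difference between arms has standard error 0.516. A one-standard-error imbalance moves the change contrast by 0.5 × 0.516 = 0.26 mm. At rho 0.95 the shift is 0.05 × 6.32 × √(2/30) = 0.08 mm. This noise is already inside the unadjusted standard error: at rho 0.5, 0.516² − 0.447² = 0.067 = 0.26². Adjustment removes it.

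**Step 5: form of the model.** Regressing change on arm and pre-operative length gives the same arm coefficient as regressing final length on them, because the two outcomes differ only by a covariate already in the model. Item 6 can stay as written.

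**The case against.** The best answer is that section 3.4.2.4 defines measurements and not a model, that the two-sample test appears only as a sizing device, and that section 4.5 leaves regression open. Covariates are often named in a statistical analysis plan, and none is at hand. Sizing on an unadjusted change and adjusting later is ordinary and conservative. Research question 2 in section 2.0 also foresees use of baseline characteristics. All of this stands. A reader might infer that the protocol commits to leaving the baseline value out; no section says so.

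A reader might also infer that chance imbalance biases the result. Under randomisation it does not, because the imbalance is noise that the standard error already covers. Nor is percentage change planned as a rival test: the text says only that it is calculated.

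The size of the gain cannot be fixed from the documents, since they give neither rho nor the SD of root length, and at rho 0.95 the gain is about one percentage point. The age range in section 3.4.1 is an eligibility limit. Section 3.4.2.1 expects most children to come from screening at 9–10 years, so the spread in root development may be narrower than the limits suggest.

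What survives is that the only comparison the protocol describes for its sized outcome is unadjusted, and that a method with the same estimand and generally better precision is available from data already collected.

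**Conclusion.** The point holds as an improvement that costs nothing; the protocol does not contain an error here. On its own inputs, with all 60 teeth followed, the unadjusted comparison meets the stated 80% power (81.5%). Adjusting for pre-operative root length would raise that to about 91% at rho 0.5, 85% at rho 0.8 or 82% at rho 0.95. These figures rest on 2 being the SD of the change, on equal pre- and post-operative variances and on an assumed rho. The direction is reliable, but the amount is not known.

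A stronger reading, that the trial is underpowered or its estimate biased because baseline is ignored, is not supported. Whether 30 per group really includes the dropout margin claimed in section 6.2 is a separate question, and adjustment should not be used to settle it.

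**What to change.** Add to section 4.5:

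- The primary root-length comparison is made in mm at 18 months by a linear model with arm and pre-operative root length. The outcome may be final length or change, since the treatment effect is the same.
- Dentinal wall thickness and apex width are analysed in the same form, each with its own pre-operative value.
- Percentage change in root length is reported descriptively and not tested.

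Further covariates such as age and pre-operative apex width are optional. If used, they should be named before the data are seen. Section 3.5 should also state the unit of the 1.5 and whether the SD of 2 refers to the change.

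The cost is a few sentences. The pre-operative measurements are already planned, so no new data, visits or patients are needed, and the sample size need not change.
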